#### **6.1.3. Data to be collected**

The following data will be collected:

- **Prespecified ultrasound findings as described in Table 2.**
- Other data to be collected: demographic characteristics: age, weight, height, parity; admission type: medical or surgical; if surgical, type of surgery; date and outcome at hospital discharge (transferred to another hospital or home, death).

#### **6.1.4. Randomization, blinding and treatment allocation**

Patients are prospectively recruited on a consecutive basis. No randomization will be performed. The reference standard operator will be blinded to the results of the ultrasound examinations made with the hand held apparatus and vice-versa.

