## 1. PROJECT SUMMARY

**Rationale:** The majority of obstetric emergencies are identified through clinical examination, which cannot be substituted by ultrasound. However, just as a laboratory exam, ultrasonography can provide swift point of care information on fetus presentation, viability, placenta position, quantity of amniotic fluid and presence of abdominal fluid to inform the clinical reasoning and therapeutic escalation. Ultrasound literature in low-resource settings has favoured antenatal care (ANC) rather than the emergency setting. Also, hand-held ultrasound machines may not be as performant as traditional machines used by expert operators but to date is still to be tested in a low resource setting.

**Objective:** to assess the *reliability* of **ultrasound findings** measured by hand held ultrasound probes used by operators with variable experience in a low resource hospital.

**Hypothesis:** There is substantial agreement between simple ultrasound findings identified using hand held ultrasound devices and the reference standard.

**Study design:** a prospective observational diagnostic accuracy study.

**Study population:** parturients admitted to the Princess Christian Maternity Hospital (PCMH) in Freetown, Sierra Leone.

**Sample size:** no formal sample size calculation is performed. Based on current rates of admissions to the PCMH we expect to perform obstetrical ultrasound scan in at least 300 patients during a 2–months study period.

**Methods:** 4 trained physicians (3 naive and 1 intermediate ultrasound users) will perform the ultrasound investigations using the hand held device and complete a structured predefined report form of obstetric ultrasound findings at patient admission or according to clinical indications after admission. These will be compared with the reference standard, i.e. an ultrasound examination performed by a specialist gynecologist/obstetrician using a conventional apparatus in the hospital ultrasound room.

**Main study parameters/primary endpoints:** The mean diagnostic accuracy among nine ultrasound obstetric findings collected with hand held devices versus the reference standard.

**Nature and extent of the burden and risks associated with participation, benefit and group relatedness:** Ultrasound is a non–invasive and painless procedure without additional risks.

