#### **4.1.4.Secondary hypothesis**

1. The diagnostic accuracy will be significantly higher for specific 'easier to detect' *individual ultrasound findings* such as intrauterine pregnancy, amniotic fluid estimation, cephalic presentation, and presence of abdominal fluid.
2. The diagnostic performance of the ultrasound *naïve operator* is significantly different from the intermediate operator only for more complex ultrasound findings such as fetal heart, presence of retroplacental hematoma, placenta location, estimation of gestational age and detection of multiple pregnancy.
3. The proportion of complete examinations is >90% and quality of images as estimated by a simple visual scoring system is high (more or equal to 3).

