##### **5.1.2.Exclusion criteria**

The following exclusion criteria will apply in the observational study:

- Ultrasound examination not feasible, e.g., due to electricity breakdown, or physical absence or unavailability of the trained sonographers.

**Table 1.** Inclusion categories as defined by National Protocols and Guidelines for Emergency Obstetric and Newborn care (14) or hospital protocol.

Inclusion criteria	Case Definition
Vaginal bleeding in early pregnancy	Vaginal bleeding or cramping, with amenorrhea or positive pregnancy test <22 weeks of gestation
Pre-eclampsia	Blood pressure $\geq 140/90$ (at least 2 recordings, 4 hours apart) PLUS any of: proteinuria (at least 2+ on dipstick, headache, generalized oedema, visual disturbance).
APH third trimester:	Vaginal bleeding after 22 weeks of pregnancy or in labour before giving birth. May have final diagnosis of abruptio placentae, placenta previa and ruptured uterus.
Prolonged/ Obstructed labour:	Prolonged latent or active phase, cephalopelvic disproportion, obstructed labor, inadequate uterine activity, prolonged expulsive phase.
High risk pregnancy in ANC	Fulfil any of the following criteria (as defined by hospital protocol): 
 
1. Previous Cesarean Section
 
2. Previous still birth
 
3. Age below 18 years
 
4. Short stature (height < 150cm)
 
5. Grand Multipara: Gravida more than 5.
 
6. Fundal Height >40cm
 
7. Suspected breech
 

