## **5.2. Sample size calculation**

Sufficient information to perform a formal sample size calculation is lacking. During a 2-month period all patients meeting the inclusion and exclusion criteria will be recruited. Based on current rates of admissions in the mentioned services, we expect to recruit at least 300 patients (75 patients per operator, 15 for each of the 5 inclusion categories) during a 2 months data collection period.

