### 6.3.2. Ultrasound procedure

Eligible patients will receive:

- a structured point of care ultrasound examination immediately at admission in emergency (or at the point of visit in ANC or ward) by the medical officer using the hand held device and following a simple checklist (Table1).
- the ultrasound examination will be repeated by an expert operator using a standard ultrasound machine in the scanner room of PCMH.

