## **7.2. Statistical analysis**

Data will be reported as mean and standard deviation or median with interquartile range (continuous data), and as frequency and percentage (categorical data). The agreement between the hand-held device and the conventional apparatus on categorical findings scoring will be assessed using diagnostic accuracy and Cohen's K statistics. When appropriate, comparison between subgroups will be performed using Student's t test, ANOVA, Mann-Whitney test or Kruskal-Wallis test for continuous data, and with Chi-square test or Fisher's test for categorical data. A p-value less than 0.05 will be considered statistically significant. Statistical analyses will be performed using R (R Foundation for Statistical Computing, Vienna, Austria). The sensitivity, specificity, positive predictive value, and negative predictive value for each dichotomous ultrasound finding acquired with hand held devices against the reference diagnoses with conventional apparatus will be assessed when appropriate. Quality of images will be assessed by standardized scoring system from 0 to 4 (0= no meaningful images; 1 = poor, not sufficient for interpretation; 2 = good, acceptable for interpretation; 3= excellent, minor suggestions for interpretations; 4 = outstanding, no suggestions for interpretations). All analyses will be conducted after the end of patient recruitment and no interim analyses are planned.

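### Nothing secures the expected even spread of case types across operators, and only unstratified tests are named for comparing naive with intermediate operators

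*Protocol*

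**What the plan says.** - **Operators and comparison.** The Project Summary (section 1) lists "4 trained physicians (3 naive and 1 intermediate ultrasound users". Secondary objective 2 (section 4.1.2) asks whether reliability differs between the two levels of experience. Hypothesis 2 (section 4.1.4) predicts that the naive operator "is significantly different from the intermediate operator only for more complex ultrasound findings such as fetal heart" and four other findings.
- **Who scans whom.** Section 6.3.2 gives each woman one hand-held scan, "immediately at admission in emergency (or at the point of visit in ANC or ward) by the medical officer using the hand held device", followed by the expert's scan on the conventional machine.
- **Assignment.** Section 6.1.4 states: "Patients are prospectively recruited on a consecutive basis. No randomization will be performed". No section gives a rule linking a woman to an operator. Section 5.1.2 excludes women when there is "physical absence or unavailability of the trained sonographers".
- **Expected numbers.** Section 5.2 says "we expect to recruit at least 300 patients (75 patients per operator, 15 for each of the 5 inclusion categories". The same paragraph says that "all patients meeting the inclusion and exclusion criteria will be recruited" over two months.
- **Tests.** For subgroup comparisons, made where appropriate, section 7.2 lists Student's t test, ANOVA, "Mann-Whitney test or Kruskal-Wallis test for continuous data, and with Chi-square test or Fisher's test for categorical data". It mentions no stratification or adjustment by inclusion category.

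**The concern.** The two operator groups see different women, so a comparison of their accuracy is fair only if the women are comparable. The five inclusion categories run from bleeding before 22 weeks to obstructed labour, and the same finding may well be harder to read in one than in another. Fetal heart, which hypothesis 2 calls complex, is scored in all five.

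If the intermediate operator's share of a hard category differs from the naive operators' share, a pooled chi-square test compares skill and case mix together. A difference could then appear where skill is equal, or a real one could be masked, and hypothesis 2 could be accepted or rejected for the wrong reason.

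**Working it through.** **1. The plan's own figure.** 4 operators × 75 = 300, 5 categories × 15 = 75, and 4 × 5 × 15 = 300, so section 5.2 is consistent. It implies 3 × 75 = 225 naive and 75 intermediate scans, with 60 women per category (45 naive, 15 intermediate). On that exact grid each group has 20% of its women in every category, and category cannot confound the comparison.

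**2. Findings exposed** (categories per finding, counted from Table 2):

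| Finding | Categories | Exposed to category mix |
|---|---|---|
| Fetal heart | 5 | yes |
| Amniotic fluid | 4 | yes |
| Cephalic presentation | 3 | yes |
| Low-lying placenta, gestational age, multiple pregnancy | 2 each | yes |
| Intra-uterine pregnancy, free fluid, retroplacental hematoma | 1 each | no |

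A composite built from these findings is exposed too.

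**3. Spurious gap with equal skill (fetal heart).** The protocol gives no accuracies, so these are assumed: 95% in four categories, and a = 85, 75 or 65% in early-pregnancy bleeding, the same for every operator. Let E of the 60 early-pregnancy women be scanned by the intermediate operator, with that operator's other women spread about evenly. Then

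gap (naive minus intermediate) = [E/75 − (60 − E)/225] × (0.95 − a).

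Rejection rates are from simulation (20,000 to 40,000 trials per scenario, two-sided 5%, Pearson chi-square on the pooled table, Mantel-Haenszel over the five categories). Triples are for a = 85/75/65%.

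| E | Intermediate share | Naive share | Gap, points | Chi-square rejects | Mantel-Haenszel rejects |
|---|---|---|---|---|---|
| 15 (section 5.2) | 20% | 20% | 0 | 3 to 5% | about 5% |
| 20 | 27% | 18% | 0.9/1.8/2.7 | 7 to 10% | about 5% |
| 22 | 29% | 17% | 1.2/2.5/3.7 | 7 to 15% | about 5% |
| 30 | 40% | 13% | 2.7/5.3/8.0 | about 15/31/48% | about 5% |

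Hand check for E = 30, a = 75%. The naive group expects 0.133 × 0.75 + 0.867 × 0.95 = 0.923 and the intermediate 0.40 × 0.75 + 0.60 × 0.95 = 0.870, pooled 0.910. The standard error is √[0.910 × 0.090 × (1/225 + 1/75)] = 0.038, so z = 0.053/0.038 = 1.40. The chance of exceeding 1.96 is about 29%, close to the simulated 31%.

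**4. The opposite direction.** If the intermediate operator worked mostly in antenatal care (70% of that operator's women, none with early-pregnancy bleeding), the gap reverses in sign and chi-square rejects in about 10/26/50%. Mantel-Haenszel again stays near 5%.

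**5. Hiding a real difference.** Assume a true intermediate advantage of about 7 to 8 points. On the even grid the crude test has 41 to 52% power and the stratified test 43 to 53%. Under a deliberately extreme mix (early-pregnancy bleeding 56% of intermediate and 8% of naive women), crude power falls to 6 to 11%, while the stratified test keeps 27 to 33%. For example, with naive accuracies of 71% (early pregnancy) and 91% (elsewhere) against 79% and 99%, the pooled values are 0.08 × 0.71 + 0.92 × 0.91 = 0.894 and 0.56 × 0.79 + 0.44 × 0.99 = 0.878. The better operator looks 1.6 points worse.

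**The case against.** - **Section 5.2 expects balance.** If 15 women per category per operator are achieved, no category bias exists. This stands, and it makes the problem conditional. But the grid is worded as an expectation, beside recruitment of every eligible woman, and consecutive arrivals need not fill 20 equal cells.
- **The imbalances are assumed.** This also stands. At 40%, one of four operators sees half of all early-pregnancy women (30 of 60). With about 25% the chi-square rejects in only 6 to 8%. A continuity correction lowers the 40% figures to about 9/22/40%. Small departures from the grid do little.
- **Stratification belongs in a SAP.** Only the protocol was available, and the absence of a Mantel-Haenszel test there is not in itself an error. Section 7.2 does, however, list the tests for subgroup comparisons, none of them stratified, and section 4.1.4 states a significance hypothesis that they would be used to test.
- **The operator endpoint may be paired.** Section 6.1.2 lists inter-observer agreement between naive and intermediate operators, which on an ordinary reading needs both to scan the same woman. Case mix would then not matter. Section 6.3.2 describes only one hand-held scan per woman, so the procedure as written gives unpaired groups.
- **A stronger reading is tempting.** From sections 5.1.2 and 6.3.2 a reader might infer that each woman goes to whoever is on duty, or that hard cases are steered to the experienced operator. The protocol says neither. It is silent on assignment, and that silence is all that can be criticised.

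**Conclusion.** The point holds in a conditional form. The naive-versus-intermediate comparison depends on a balance of case types that section 5.2 expects and no section secures, and the tests named in section 7.2 do not protect against its absence.

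The size depends on the imbalance: none on the expected grid, a false-positive rate of about 7 to 15% with a moderate shift, and about 15 to 48% with a large one. All accuracies and case mixes behind these figures are assumptions, and only fetal heart was simulated. For the other multi-category findings and the composite, exposure follows from Table 2 but has not been sized.

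A reader might infer that the operator comparison is already invalid, or that the study's main result is at risk. Neither follows. The bias arises only if mixes differ, the primary endpoint pools operators, and intra-uterine pregnancy, free fluid and retroplacental hematoma cannot be affected by category mix. This is a worthwhile, low-cost improvement to a secondary analysis.

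**What to change.** Add to section 7.2 that naive-versus-intermediate comparisons of fetal heart, amniotic fluid, presentation, placental position, gestational age, multiple pregnancy and the composite are made within inclusion category, by a Mantel-Haenszel test or a logistic model with category as a factor. For the composite, to which each woman contributes several findings, form the difference within category first and combine with common weights. Report each operator's number of women per category beside the result.

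Category determines each woman's checklist, so no new data are needed. The cost is a slightly wider interval, and any category seen by only one operator group drops out of the comparison. On the even grid the simulations show no loss of power.

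Two limits remain. Women may still differ between operators within a category, and with one intermediate operator, experience cannot be separated from that individual. A rota that brings recruitment nearer to the section 5.2 grid is optional where immediate scanning allows it, and the fix does not depend on it.

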### **6.2. Study groups**

Not applicable.

### **6.3. Study procedures**

#### **6.3.1. Training of operators**

The ultrasound operators will receive a 2-week training course. The 1st week training consists of lectures on basic science of ultrasound and tomography, demonstrations by an expert obstetrics sonographer, and hands-on practice at the scanning room of PCMH. The second week of training will focus on how to operate the hand-held ultrasound device, training on the standard operating procedure (SOP) and case report form (CRF) completion.

**Table 2. Ultrasound findings.** Abbreviations: GA, gestational age; FH, fetal heart; MVP, maximum vertical pocket, APH, antepartum hemorrhage; ANC, antenatal clinic.

	Inclusion category	Finding 1	Finding 2	Finding 3	Finding 4
1	Vaginal bleeding in early pregnancy	Intra-uterine pregnancy: yes/no	FH: yes/no	Free fluid in abdomen: yes/no	None
2	Pre-eclampsia	FH: yes/no	Amniotic fluid MVP<2cm: yes/no	GA: ≤34 or >35 weeks	Cephalic presentation: yes/no
3	APH in third trimester	Placenta low lying: yes/no	FH: yes/no	Retroplacental hematoma: yes/no	Amniotic Fluid MVP<2cm: yes/no
4	Prolonged/ obstructed labor	FH: yes/no	Multiple pregnancy: yes/no	Cephalic presentation: yes/no	Amniotic Fluid MVP<2cm: yes/no
5	ANC High Risk Pregnancy*	Cephalic presentation: yes/no	Multiple pregnancy: yes/no	FH: yes/no	Amniotic Fluid MVP<2cm: yes/no
				Placenta low lying: yes/no	GA: ≤34 or >35 weeks

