#### 7. Image Processing

7.1 Line interpolation	
7.2 Frame correlation	

#### 8. Estimated lifetime with appropriate use

7 years

The device “US-304” can be connected to the smartphone which fulfills certain requirements. Any smartphone run by Android OS can be used for the portable ultrasound device after the application developed by the same manufacture to run the program for ultrasound examination is installed. Once the application is installed in the smartphone, it will be an interface to control the device to optimize the images acquired by ultrasound examinations and to perform obstetric calculations for estimation of gestational ages based on the measurements of bi-parietal diameter (BPD) or femur length (FL). In the study, the ultrasound device (probe type: convex type with 3.5 MHz) and a smartphone (ASUS; Taiwan), in which the application has already been installed, will be provided for practical training sessions.

The manufacture information is given below:

Lequio Power Technology Corp.

[name]

[contact] [contact]

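### Gestational age is specified for collection only as a two-class finding; recording it in weeks from both scans would recover lost information at little cost and leave the primary endpoint unchanged.

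*Protocol*

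**What the plan says.** Table 2 (protocol section 6.3.1) gives gestational age as "GA: ≤34 or >35 weeks" in two of the five inclusion categories, pre-eclampsia and high-risk pregnancy in ANC. The data list in section 6.1.3 takes "Prespecified ultrasound findings as described in Table 2" and names no gestational age in weeks, BPD or FL. Section 7.2 assesses categorical findings by diagnostic accuracy and Cohen's kappa, and compares subgroups on categorical data by chi-square or Fisher's test.

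Section 3.2 says that hand-held devices can estimate gestational age from BPD or FL. The last part of the Appendix says the same of the application used in this study. For the reference, section 6.3.2 says only that "the ultrasound examination will be repeated by an expert operator using a standard ultrasound machine".

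The second secondary hypothesis (section 4.1.4) expects naive and intermediate operators to differ significantly on the more complex findings, among them "placenta location, estimation of gestational age and detection of multiple pregnancy". The summary names three naive operators and one intermediate operator. Section 5.2 gives no power for any comparison and expects "75 patients per operator, 15 for each of the 5 inclusion categories".

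**The concern.** A two-class result carries information only about women near the cut. A scan that reads 32 weeks when the reference reads 28 is wrong by 4 weeks and counts as correct. An error of 0.3 weeks across the cut counts as wrong. Real differences in dating between operators, or between devices, can therefore leave class accuracy almost unchanged.

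Two things are at stake. A non-significant class comparison could be read as showing that experience does not matter for dating, when the test could hardly have shown otherwise. And consistent over- or under-dating by the hand-held device could not be expressed in weeks; only the direction of misclassification across the cut would be visible. The choice has to be made at data collection, because weeks that were never written down cannot be restored by a later analysis plan. The offline expert review in section 7.3 covers only 20 examinations.

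**Working it through.** **Numbers of scans.** Section 5.2: 4 operators × 5 categories × 15 = 300, which matches the stated total. Gestational age is scored in 2 categories, so 2 × 15 = 30 scans per operator: 30 intermediate, 3 × 30 = 90 naive, 120 in all.

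**Assumptions (the protocol gives none).** Reference error SD 1.0 week. True gestational age normal, mean 32 to 36 and SD 3 to 5 weeks. One cut at 34.5 weeks, used only to make the arithmetic possible. Two-sided 0.05. Scans independent, and operators within a level alike.

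**Model.** With true age T, reference R = T + e_R and hand-held H = T + e_H. A scan is correct when R and H fall on the same side of the cut. In weeks, the measure is |H − R|, and SD(H − R) = √(σ_H² + 1²). For σ_H = 1 this is √2 = 1.41 weeks; for σ_H = 2 it is √5 = 2.24 weeks, a ratio of 1.58. At mean 34 and SD 4 weeks, the same change moves class accuracy only from about 89% to about 83.5%.

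**Check of that case by formula.** Pooled proportion = (0.89 × 30 + 0.835 × 90)/120 = 0.849. SE under no difference = √(0.849 × 0.151 × (1/30 + 1/90)) = 0.0755. SE under the difference = √(0.89 × 0.11/30 + 0.835 × 0.165/90) = 0.0692. Power = Φ((0.055 − 1.96 × 0.0755)/0.0692) = Φ(−1.34), about 9%.

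**Simulated power, intermediate versus naive** (with 1,500 runs the standard error is at most about 1.3 points):

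| Error SD, weeks | Chi-square on class | Mann-Whitney on absolute difference in weeks |
|---|---|---|
| 1.0 vs 2.0 | 7–11% | 62–67% |
| 1.5 vs 2.5 | 7–10% | 51–56% |
| 1.0 vs 2.5 | 11–18% | 91–93% |
| equal | near 5% | near 5% |

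**Naive bias instead of extra scatter** (separate run: no reference error, age about N(34, 4) or N(36, 3) truncated to 24–42 weeks). A 1-week naive bias with SD 1 to 2 gives Fisher power of 2–5%, against 64–99.7% for a t test on the signed difference. Mann-Whitney on the absolute difference gives only 8–63% there, so both the signed and the absolute difference are needed.

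**Precision of the mean difference in weeks.** Half-width of the 95% interval = t × SD/√n. For n = 120 and SD 1, 1.5, 2 and 3 weeks: ±0.18, ±0.27, ±0.36 and ±0.54. For one operator (n = 30): ±0.37 at SD 1 to ±1.12 at SD 3.

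**Class test against accuracy gaps directly** (same power formula, 30 vs 90). 95% vs 80%: 48%. 95% vs 75%: 72%. 95% vs 70%: 88%.

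**Is a scan-level test in weeks safe?** Simulated with no experience effect but with operators who differ (assumed: error SD varying by 20–40% around 1.5 weeks, operator bias SD 0–1 week, 30 scans each). Mann-Whitney on weeks rejected in 11–31% of runs and chi-square on class in 6–9%, against a nominal 5%.

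**The case against.** The study is about simple, prespecified findings, and the class is the finding. Amniotic fluid is likewise cut at a fixed depth. No objective, hypothesis or endpoint asks for dating bias in weeks. This stands: class accuracy is a legitimate target, belongs in the composite endpoint and should stay. The hypothesis is nonetheless worded in terms of estimating gestational age, and the class is a coarse measure of that.

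A reader might infer that both scans are documented as measured in weeks and that the weeks are then discarded. The documents do not go that far. An estimate in weeks is stated for the hand-held application and only implied for the reference scan. The CRF is not shown and may hold the weeks. The device specification mentions recording of measurement results, and the expert's report goes into the patient's chart (section 7.1.2). What can be said is that Table 2 and section 6.1.3 do not ask for weeks.

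A reader might also infer that the class test has almost no power whatever the truth. That depends on the effect: for accuracy gaps of 15 to 25 points from 95%, power is 48 to 88%. Under the assumed error model such gaps are hard to reach. Even SD 3 versus 1 week without bias gave only 32–37% power on class in the separate run. But the SDs are assumptions.

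Finally, it is tempting to make a test in weeks the formal test of experience. With one intermediate operator this is not supported: the person and the experience level are inseparable, and the inflated rejection rates above follow. The part of the 51–93% that reflects experience rather than the individual operator is unknown.

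**Conclusion.** The point holds as a cheap improvement. Gestational age is specified for collection only as a class, and under the stated assumptions this costs most of the information on dating error: about 7–18% power on class against about 51–93% on the same scans in weeks, if operators within a level are alike. A mean dating shift cannot be estimated in weeks from classes, whereas recorded weeks would give it to within ±0.18 to ±0.54 weeks for SDs of 1 to 3 weeks.

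The scope is one of nine findings and one secondary hypothesis; the primary endpoint is not at fault. Low power for the operator comparison also comes from having one intermediate operator with 30 such scans, which recording weeks does not cure. The ages left unclassified between 34 and 35 weeks are a separate matter: closing that gap would not restore the lost information.

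**What to change.** - **Table 2 and section 6.1.3 (and the CRF):** record gestational age in weeks and days, with BPD and/or FL, from both the hand-held and the conventional scan, and derive the class from it. If the CRF already holds these fields, say so in section 6.1.3.
- **Section 7.2:** keep class accuracy for the composite primary endpoint. Add the mean hand-held minus reference difference with 95% limits of agreement, and the absolute difference, overall and for each of the four operators.
- **Second secondary hypothesis:** present the naive-versus-intermediate comparison in weeks as descriptive. State that one intermediate operator cannot be separated from the experience level, and do not use a scan-level Mann-Whitney test as a test of experience.

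The cost is one or two extra numeric fields per scan and one extra summary. No further scans, patients or staff are needed.

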## **6. METHODS**

### **6.1. Study parameters/endpoints**

#### **6.1.1. Main study parameter/endpoint**

The primary endpoint is the mean aggregated diagnostic accuracy between the ultrasound findings collected via hand held devices as compared to the conventional apparatus.

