#### **6.1.2. Secondary study parameters/endpoints**

1. Detailed diagnostic accuracy for each of the nine ultrasound findings.
2. Inter-observer agreement on ultrasound findings between naïve and intermediate operators.
3. Mean 'quality of image score' (0-4) for each of the nine ultrasound findings.
4. Proportion of complete ultrasound examinations i.e. with all pre specified findings allocated for the category being completed.

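### Table 2 codes gestational age as two categories with a one-week gap and gives no rule for readings that fall in it

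*Protocol*

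**What the plan says.** Table 2, printed under Protocol section 6.3.1, lists the findings to be scored in each inclusion category. For pre-eclampsia and for high-risk pregnancy in antenatal care, the GA item reads "GA: ≤34 or >35 weeks". Every other finding in the table is a yes/no item. Section 6.1.3 makes Table 2 the definition of the ultrasound data to be collected.

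Section 7.2 states that agreement on "categorical findings scoring will be assessed using diagnostic accuracy and Cohen's K statistics", and adds sensitivity, specificity, positive and "negative predictive value for each dichotomous ultrasound finding acquired with hand held devices".

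The primary endpoint is given in the project summary as "The mean diagnostic accuracy among nine ultrasound obstetric findings collected with hand held devices versus the reference standard" and in section 6.1.1 as the "mean aggregated diagnostic accuracy". Section 6.1.2 adds "Detailed diagnostic accuracy for each of the nine ultrasound findings", and a completeness endpoint that requires every finding allocated to the category to be filled in. Section 4.1.4 places "estimation of gestational age and detection of multiple pregnancy" among the complex findings on which naive and intermediate operators are expected to differ, and expects more than 90% of examinations to be complete.

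The Appendix says that the phone application serves "to perform obstetric calculations for estimation of gestational ages based on the measurements of bi-parietal diameter (BPD) or femur length (FL". GA is therefore obtained as a continuous estimate.

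**The concern.** The two GA options do not cover all possible readings. In decimal weeks, anything above 34 and up to 35 fits neither option. In completed weeks, week 35 fits neither. Each woman has two readings, one per device, so a pair cannot be classified if either falls in the gap. These are the pairs closest to the boundary, where two imperfect measurements are most likely to land on opposite sides.

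The analysis in section 7.2 needs a two-by-two table, and as coded some pairs have no cell in it. The outcome depends on what the examiners or analysts improvise:

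- **Dropped:** difficult pairs leave the denominator, and accuracy and kappa for GA rise.
- **Forced into a category without a rule:** the two examiners, blinded to each other under section 6.1.4, may code the same week differently. That disagreement has nothing to do with the device.
- **Left blank:** the examination fails the completeness criterion for a reason unrelated to feasibility.

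This is not detail that a later analysis plan could supply. If the case report form follows Table 2 and offers only these two options, the information is lost at the bedside.

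**Working it through.** **Expected numbers.** Section 5.2 gives at least 300 patients, 75 per operator and 15 per category per operator. With four operators and five categories, 4 × 75 = 4 × 5 × 15 = 300, which reproduces. GA is scored in two categories: 2 × 15 × 4 = 120 expected patients, of whom 2 × 15 = 30 belong to the one intermediate operator. These are expectations. Recruitment is consecutive and has no category quotas.

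**Share of true GA in the gap.** The documents give no GA distribution or measurement error, so everything below rests on assumptions.

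- Uniform on [a, b]: 1/(b − a). For 24–41, 28–40 and 32–38 weeks this is 1/17 = 5.9%, 1/12 = 8.3% and 1/6 = 16.7%.
- Normal with mean μ and SD σ: Φ((35 − μ)/σ) − Φ((34 − μ)/σ). For (34, 4), (36, 3), (32, 5) and (37, 2.5) this is 9.9%, 11.7%, 7.0% and 9.7%. For mean 28 and SD 6–7 it is about 4%.

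**Effect of dropping gap pairs.** By simulation, each reading is true GA plus independent normal error. Accuracy with a single cut at 34 on all pairs is compared with accuracy after removing pairs in which either reading lies in (34, 35]. The cut at 34 is only a comparator. Selected scenarios, with error SDs in weeks (hand-held/reference) and differences subject to rounding:

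| True GA | Error SD | Pairs touching gap | Accuracy, all pairs | Accuracy, gap pairs dropped | Difference (points) |
|---|---|---|---|---|---|
| Uniform 24–41 | 1/0.5 | 9.8% | 94.8% | 98.5% | 3.7 |
| Uniform 28–40 | 1.5/1 | 14.8% | 88.0% | 93.6% | 5.6 |
| Uniform 32–38 | 1/0.5 | 27.6% | 85.3% | 94.8% | 9.5 |
| Uniform 32–38 | 1.5/1 | 28.6% | 77.2% | 85.1% | 7.9 |
| Normal (34, 4) | 1/1 | 16.6% | 89.0% | 95.3% | 6.3 |
| Normal (32, 5) | 1/1 | 12.0% | 91.8% | 96.8% | 5.0 |
| Normal (37, 2.5) | 1/1 | 16.7% | 91.1% | 95.4% | 4.3 |
| Normal (37, 2.5) | 3/2 | 16.5% | 77.3% | 78.8% | 1.5 |

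With mean 28 and SD 6–7, only about 6–7% of pairs touch the gap. Across everything examined, the share of pairs touched is about 6–29%, that is 0.06 × 120 ≈ 7 to 0.29 × 120 ≈ 35 pairs. For the intermediate operator it is about 2 to 9 of 30. The change in accuracy is upward every time, by about 1.5–10 points. In the twelve uniform scenarios kappa rises by about 0.07–0.22. Reading the code in completed weeks gives nearly the same results.

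**Effect of forcing.** In the four normal scenarios with error SD 1/1, assigning gap readings to a side at random gives 86–91% accuracy, against 88–92% with the single cut at 34.

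**Effect on the primary endpoint.** If the nine findings are averaged without weights, the shift is the GA shift divided by nine: 1.5/9 ≈ 0.2 to 9.5/9 ≈ 1.1 points. If readings are pooled, the expected total is 60 × (3 + 4 + 4 + 4 + 6) = 1,260. GA is 120/1,260 = 9.5% of it, so the effect is of the same order.

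**Effect on completeness.** If about 4–17% of hand-held GA readings lie in the gap and are left blank, then 120/300 × 4% = 1.6% to 120/300 × 17% = 6.8% of all examinations become incomplete on this account alone. The hypothesis of more than 90% complete leaves less than 10% in all.

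**The case against.** The strongest reply has four parts.

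First, a reader might infer that the protocol removes the hardest cases and so overstates accuracy. The text does not support that. No passage says gap readings are dropped, and the other two outcomes carry no demonstrated upward bias. A blank would be visible and would count against the device in the completeness result. This part stands, and the inflation is conditional.

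Second, a reader might infer that the primary endpoint is materially biased because GA is one of its nine components. It is not: the composite moves by about 0.2–1.1 points. At an assumed 90% accuracy and with 1,260 readings treated as independent, the 95% half-width is 1.96 × √(0.9 × 0.1/1,260) ≈ 1.7 points, which is larger than the shift. This also stands.

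Third, the size depends on assumptions. Several antenatal entry criteria in Table 1, such as previous caesarean section, age below 18 and short stature, are not tied to late pregnancy, so fewer readings may fall near the gap. Most hand-held operators are naive, so an error SD of 1 week may be too small. Both points stand, and they are why the range is wide. The direction does not change.

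Fourth, it may be a typing slip. If the second option was meant as 35 or more completed weeks, the categories are exhaustive. That is possible, but the same wording appears in both rows and nothing in the protocol corrects it. Examiners will work from what is printed.

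**Conclusion.** The point holds: the GA coding is wrong as written, and the correction should be made before enrolment. The gap is a fact of the text under either reading of weeks, and it conflicts with an analysis that treats the findings as dichotomous.

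The size is conditional. If gap pairs are dropped, GA-specific accuracy rises by about 1.5–10 points and kappa rises with it. If they are forced or left blank, the harm is arbitrary misclassification or spurious incompleteness. The damage falls mainly on GA-specific accuracy and kappa, on the naive-versus-intermediate comparison for a finding the protocol itself names as complex, and on completeness. The effect on the primary composite is small. All figures depend on the assumed spread of GA and on independent normal measurement errors. Only the existence of the gap, and the lack of a rule for it, are certain.

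**What to change.** Reconcile the two limits in both GA cells of Table 2 into one exhaustive, non-overlapping cut: GA ≤ c versus GA > c, with c stated in weeks and days and chosen by the investigators. State that the same cut applies to the hand-held and the reference scan. Record the GA from each device in weeks and days on the case report form, so that every pair can be classified whatever the examiner ticks.

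The cost is two edited table cells and one numeric field per scan. The hand-held application already computes GA. The reported GA accuracy may come out lower than if boundary pairs had been dropped. With numeric values recorded, a mean difference with limits of agreement could also be reported, but that is optional and is not needed to close the gap.
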